#### 5.5.1.1. Liver Chemistry Stopping Criteria, Participant Management and Follow-Up

Participants who develop ALT  $\geq 5$ xULN must be followed weekly until resolution or stabilization (ALT  $< 5$ xULN on 2 consecutive evaluations).

##### When any of the liver chemistry stopping criteria is met, do the following:

- Immediately hold IP. If on LA therapy, **do not** administer another injection until approval is received from the ViiV Safety and Labelling Committee.
- Report the event to the Medical Monitor within 24 hours of learning its occurrence (Section 7.4.3.4).
- Complete the liver event eCRF and SAE eCRF, where applicable, (see Section 7.4.3.4)
- Complete the liver imaging and/or liver biopsy eCRFs if these tests are performed.
- Perform liver event follow up assessments (described below), and monitor the participant until liver chemistries resolve, stabilize, or return to Baseline values as described below.
- Make every reasonable attempt to have participants return to clinic within 24 hours for repeat liver chemistries, liver event follow up assessments (see below), and close monitoring.
- A specialist or hepatology consultation is recommended.
- Monitor participants twice weekly until liver chemistries (ALT, AST, alkaline phosphatase, bilirubin) resolve, stabilize or return to within Baseline values.

Make every attempt to carry out the **liver event follow up assessments** described below:

Viral hepatitis serology including:

- Hepatitis A immunoglobulin M (IgM) antibody;
- Hepatitis B surface antigen (HBsAg) and Hepatitis B Core Antibody (IgM);

- Hepatitis C RNA;
- Hepatitis E IgM antibody;
- Cytomegalovirus IgM antibody;
- Epstein-Barr viral capsid antigen IgM antibody (or if unavailable, obtain heterophile antibody or monospot testing);
- Syphilis screening;
- Drugs of abuse screen including alcohol;
- Serum acetaminophen test (APAP adduct test). The site must contact GSK when this test is required. Please refer to the central laboratory manual.
- Blood sample for pharmacokinetic (PK) analysis, obtained within 60 hours of last dose. Record the date/time of the PK blood sample draw and the date/time of the last dose of investigational product prior to blood sample draw on the eCRF. If the date or time of the last dose is unclear, provide the participant's best approximation. If the date/time of the last dose cannot be approximated OR a PK sample cannot be collected in the time period indicated above, do not obtain a PK sample. Instructions for sample handling and shipping are in the SPM.
- Serum creatine phosphokinase (CPK) and lactate dehydrogenase (LDH);
- Fractionated bilirubin, if total bilirubin is greater than 1.5xULN;
- Obtain complete blood count with differential to assess eosinophilia;
- Anti-nuclear antibody, anti-smooth muscle antibody, and Type 1 anti-liver kidney microsomal antibodies, and quantitative total immunoglobulin G (IgG or gamma globulins);
- Liver imaging (ultrasound, magnetic resonance, or computerized tomography) and/or liver biopsy to evaluate liver disease; complete Liver Imaging and/or Liver Biopsy CRF forms.
- Record the appearance or worsening of clinical symptoms of hepatitis, or hypersensitivity, fatigue, decreased appetite, nausea, vomiting, abdominal pain, jaundice, fever, or rash as relevant on the AE report form;
- Record use of concomitant medications, acetaminophen, herbal remedies, other over the counter medications, or putative hepatotoxins, on the concomitant medications report form. Record alcohol use on the liver event alcohol intake case report form.

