### **6.3. Dosage and Administration**

Participants will be randomly assigned to receive treatment with Oral CAB 30 mg + RPV 25 mg once daily for 4 to 5 weeks during the Oral Phase, followed by CAB LA 600mg + RPV LA 900mg IM at Week 4b, CAB LA 400mg + RPV LA 600 mg IM at Week 8 and Q4 weekly thereafter, or to remain on their current ART. Regardless of treatment arm assignment, the investigator should instruct all participants on the importance of treatment adherence. This study has an open-label design. Dosing is outlined in [Table 5](#) below.

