**It is important to note that keeping to the participant’s visit schedule is a very important component to the study.**

**Note: All decisions regarding dose interruption / resumption must be discussed with the medical monitor in advance.**

### **6.9.1. IM Dosing**

Participants receiving CAB LA and/or RPV LA are anticipated to be at risk for development of virologic resistance if ART is interrupted. The time period during which participants are at risk for development of virologic resistance may be determined by the period between when drug levels fall below therapeutic values and when they fall below levels which exert selective pressure on HIV. This time period will vary by ART agent and is dependent upon effective concentration, inhibitory concentration, and half-life. Plasma concentrations of both LA drugs may be measurable for more than one year following IM injections. Any interruption in IM dosing should be discussed with the Medical Monitor. Investigators should ensure that the participant initiates alternative highly active ART to minimize the risk of developing resistance as concentrations of CAB and RPV decline over time.

IM dosing is expected to occur during the week in which the participant’s projected visit falls (as according to the date of the first injection). The first injections are administered at Week 4b (can be performed as soon as lab results from Week 4a become available), and the second injections are given at Week 8. The dosing window for the second injections allows administration between Week 7 and Week 8, but not later than Week 8. The dosing window for the third injections allows administration between Week 11 and

Week 12 but not later than Week 12. For subsequent injection visits, an additional (+ or -) 7 day window, from the projected visit date, is allowable for IM dosing but also not preferred. In addition, starting after the Week 12 injection, efforts should be made to limit time between injection visits to a maximum of 5 weeks. The Medical Monitor must be contacted if the length of time between injections exceeds or is projected to exceed 5 weeks. For the duration of the study, the injection visit schedule should be maintained according to the first IM injections given at Week 4b.

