## 6.11. Treatment of Study Treatment Overdose

For participants receiving Oral CAB, any tablet intake exceeding a total daily dose of 30 mg will be considered an overdose. For participants receiving oral RPV, any dose exceeding a total daily dose of 25 mg will be considered an overdose.

For CAB LA and RPV LA, any single dose in excess of the studied doses will be considered an overdose.

Should IM maladministration, specifically overdose or inadvertent IV dosing, be suspected at any time, the participant will stay onsite for approximately 2-3 hours post dose for safety monitoring and an ECG will be performed at 2 hours post dose. The Medical Monitor will be notified in the event of a suspected maladministration.

In the event of suspected maladministration, additional PK samples will be drawn at 2 hours post dosing for evaluation of CAB and RPV concentrations.

For the purposes of this study, an overdose is not an AE (refer to Section 12.6.1 ) unless it is accompanied by a clinical manifestation associated with the overdose. If the clinical manifestation presents with serious criteria, the event is a SAE (see Section 12.6.2).

If an overdose occurs and is associated with an adverse event requiring action, all study medications must be temporarily discontinued until the adverse event resolves.

The Investigator should use clinical judgement in treating overdose, as ViiV Healthcare is unable to recommend specific treatment.

In the event of an overdose the investigator or treating physician should:

1. Contact the Medical Monitor immediately
2. Closely monitor the participant for adverse events (AEs)/serious adverse events (SAEs) and laboratory abnormalities until the IP can no longer be detected systemically (at least 5 days for oral CAB and oral RPV, and 52 weeks for CAB LA and RPV LA)
3. Obtain a plasma sample for pharmacokinetic (PK) analysis if possible within 2 days from the date of the last dose of study treatment if requested by the Medical Monitor (determined on a case-by-case basis).
4. Document the quantity of the excess dose as well as the duration of the overdosing in the CRF.

Decisions regarding dose interruptions or modifications will be made by the investigator in consultation with the Medical Monitor based on the clinical evaluation of the participant.

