##### **7.5.1. PK Sample Collection**

Blood samples for evaluation of CAB (2mL each) and RPV (2mL each) plasma PK concentrations will be collected from all participants randomized to receive CAB + RPV as described in Table 8.

At Week 4b (and Week 56b for participants transitioning into the Extension Phase from the current ART arm), PK samples must be collected within the window of 20-28 hours after the last oral dose of CAB + RPV was taken the day prior to the clinic visit. Participants will take their final dose of oral CAB + RPV in the clinic at Week 4b (or Week 56b) after the pre-dose PK sample.

Participants will be expected to complete a PK dosing diary card noting the date and time of the last three oral doses of IP prior to the scheduled clinic visits at Week 4b (or Week 56b). The information from the diary card and the actual date and time of the PK samples will be recorded in the eCRF. Additionally, dosing information on the clinic day, including dosing and the actual date and time of the PK samples, must be recorded

on the eCRF. Participants will take their last dose of oral CAB + RPV in the clinic at Week 4b (or Week 56b) after the pre-dose PK sample.

PK concentrations will be summarized and used to evaluate potential exposure-response relationships.

The timing of PK samples may be altered and/or PK samples may be obtained at additional time points to ensure thorough PK monitoring.

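### The liver-event PK sample is barred beyond 60 hours after the last dose, with no separate wording for participants on 4-weekly injections

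*Protocol*

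**What the plan says.** Section 5.5.1.1 of the Protocol lists what a site does once a liver stopping criterion is met. One follow-up assessment is a "Blood sample for pharmacokinetic (PK) analysis, obtained within 60 hours of last dose". The site records the times of the last dose and of the draw. If the time of the last dose cannot be estimated, or if "a PK sample cannot be collected in the time period indicated above, do not obtain a PK sample".

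The list is not limited to tablets. Its first item tells sites that a participant on LA therapy must not be given a further dose, with the instruction not to "administer another injection until approval is received from the ViiV Safety and Labelling Committee". No other section gives injected participants a different window for this sample.

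Elsewhere the Protocol treats the two formulations differently:

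- Section 6.3 gives the injectable schedule as "CAB LA 400mg + RPV LA 600 mg IM at Week 8 and Q4 weekly thereafter".
- Section 6.9.1 says that after Week 12 "efforts should be made to limit time between injection visits to a maximum of 5 weeks", and that "Plasma concentrations of both LA drugs may be measurable for more than one year following IM injections".
- Section 6.11, on overdose, sets monitoring until the product is no longer detectable as "at least 5 days for oral CAB and oral RPV, and 52 weeks for CAB LA and RPV LA".
- Section 7.5.1 says in general terms that "PK samples may be obtained at additional time points to ensure thorough PK monitoring".

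**The concern.** A limit of 60 hours is easy to meet with a daily tablet and hard to meet with a monthly depot injection. For an injected participant the wording is a prohibition, not a preference. Once two and a half days have passed since the last injection, the site is told not to draw the sample, even though exposure may still be rising.

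Drug-induced liver injury is the first CAB risk listed in Section 4.8.1. Section 5.5.1 says the stopping criteria serve in part to establish the cause of liver events. Section 5.5.1.2 says all stopping cases go to adjudication on uniform data. Under this rule a case arising in the oral lead-in would normally have a concentration taken at the event, while an injection-phase case often would not. A concentration not taken at the time of the event cannot be recovered later.

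**Working it through.** The Protocol states no percentage on this point, so there is no figure of its own to reproduce.

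**Inputs**

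- Sampling window: 60 h (Section 5.5.1.1).
- Injection interval: 4 weeks (Section 6.3). After Week 12 a window of plus or minus 7 days is allowed and intervals are to be held to 5 weeks (Section 6.9.1), so the range is taken as 3 to 5 weeks.
- Median tmax on Q4W dosing in LATTE-2: CAB LA 6.9 days (Table 3); RPV LA 6.0 to 6.99 days (Table 4).
- LA persistence: 52 weeks (Section 6.11); possibly more than a year (Section 6.9.1).
- One stopping criterion: ALT from 5 to below 8 times ULN lasting at least 2 weeks (Section 5.5.1).

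**1. Share of the dosing interval inside the window** = 60 / (weeks × 168 h)

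- 4 weeks: 60/672 = 8.9% inside, 91.1% outside.
- 5 weeks: 60/840 = 7.1% inside, 92.9% outside.
- 3 weeks: 60/504 = 11.9% inside, 88.1% outside.

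**2. Against the time of peak concentration**

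- CAB LA: 6.9 × 24 = 165.6 h, and 60/165.6 = 36%.
- RPV LA: 6.0 × 24 = 144 h to 6.99 × 24 = 167.8 h.

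The window closes at well under half the median time to peak for either drug.

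**3. Against persistence**

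52 weeks × 168 h = 8,736 h, and 60/8,736 = 0.7%.

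**4. Against the criterion that requires persistence**

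Suppose an ALT in that range is first seen at an injection visit and that injection is given. The 2-week condition is then met no earlier than 14 × 24 = 336 h after the injection, beyond 60 h, unless a further injection has been given in the meantime.

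**5. The same rule on daily tablets**

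An adherent participant took the last tablet at most 24 h before being told to stop. Section 5.5.1.1 seeks a return within a further 24 h, and 24 + 24 = 48 h is inside 60 h. The window fits daily dosing. That it was written for daily dosing is an inference; the Protocol does not say so.

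**6. What other samples provide (Table 8 and the text below it)**

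- Pre-dose samples at Week 4b and then every 4 weeks from Week 8 to Week 52, and one-week post-dose samples at Weeks 5 and 41. These are tied to visits, not to events.
- Stored samples at Weeks 64, 72, 80 and 88; scheduled samples at Week 96.
- For participants switching from current ART, a separate row lists Weeks 56b and 60, withdrawal and stored follow-up samples.
- A withdrawal sample as soon as feasible, with no 60-hour limit, but only once withdrawal is decided.
- Stored samples in long-term follow-up at Months 1, 3, 6, 9 and 12.

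None of these, nor the general clause in Section 7.5.1, is written as an exception to the prohibition in Section 5.5.1.1.

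**The case against.** The strongest reply is that the consequence is smaller than the percentage suggests. Much of that reply stands.

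- A reader might take 91% as the share of liver events left without a sample. The document does not support that. It is a share of clock time and would carry over to events only if they were detected uniformly across the interval. Scheduled visits are mostly injection visits. An abnormality found on blood drawn that day could be followed up inside 60 hours if results return quickly. Laboratory turnaround is not stated, so the proportion is unknown.
- A reader might infer that nearly all injection-phase events have no concentration, or that the exposure evidence for causality is removed. Neither is shown. Up to Week 52 an elevation found at a 4-weekly visit has a PK sample from the same visit. Section 5.5 requires discontinuation when no compelling alternate cause is found, which brings in the withdrawal sample. Stored samples can be assayed later, and population PK may supply individual estimates (Section 9.4.4).
- It would also be wrong to say that switchers have no samples after Week 60 other than at withdrawal. Their row includes stored follow-up samples, and the first row of Table 8 is headed as covering everyone receiving the injections.
- No between-arm comparison is biased, since CAB and RPV are not sampled in participants on current ART. No primary or secondary endpoint in Section 3 is defined on this sample. How far adjudication relies on a concentration is left to a charter that is not shown.

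What does not stand is the suggestion that these provisions cure the problem. A site reading a specific instruction not to sample would reasonably follow it over a general permission elsewhere. The withdrawal sample does not serve a participant whose injections are held while the cause is investigated.

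**Conclusion.** The point holds as a defect of wording with a modest consequence. The liver-event rule applies a 60-hour limit and a flat prohibition to participants on injections. For them the window covers 8.9% of a 4-week interval (7.1% to 11.9% over 5 to 3 weeks) and ends before the median peak. It is out of line with Sections 6.9.1 and 6.11, which recognise long persistence, and with Section 7.5.1, which allows extra samples and a withdrawal sample without that limit.

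As written, it bars an event-timed sample for many injection-phase events, including those that meet the 2-week criterion more than 60 hours after the last injection. The number affected cannot be derived from the document. The percentages are shares of time and assume nothing about when events occur. The tmax figures are LATTE-2 medians with wide individual ranges, and persistence beyond a year is described as possible and as seen in some participants, not in all.

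**What to change.** Reconcile Section 5.5.1.1 with Sections 6.9.1, 6.11 and 7.5.1:

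- Limit the 60-hour condition, and the instruction not to obtain the sample, to participants who have received only oral CAB + RPV.
- For anyone who has had at least one injection, draw the CAB and RPV sample at the liver-event follow-up visit whatever the time since the injection. Record the date and time of the last injection and of the sample.

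This changes a sampling instruction only; no dose, stopping rule or restart rule is touched. Blood is already drawn at that visit, and the assays and the recording of dose and sample times are already provided for. The added cost is a few extra small tubes (2 mL per drug under Section 7.5.1) and the assays, plus a one-sentence amendment.

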#### **5.5.1.2. Liver Event Adjudication Committee**

A liver safety panel will be used to evaluate all participants who meet liver stopping criteria. Uniform sets of data and standards for adjudication will be applied across cases to inform outcomes. Full details of the analysis, timing, and the decision criteria will be pre-specified in an Adjudication Committee Charter.

### 5.5.1.3. Liver Chemistry Stopping Criteria – Restart/Rechallenge

Participants who meet liver toxicity stopping criteria should not be retreated with investigational product unless an exemption has been approved by the ViiV Safety and Labeling Committee (VSLC). The guideline for Rechallenge/Restart approved by the VSLC, which is maintained as a separate document (See Section 12.3, Appendix 3) must be followed.

#### 5.5.1.3.1. *Drug Restart/Rechallenge. Following Liver Events that are Possibly Related to IP*

- Approval by the VSLC for drug restart or additional IM administration can be considered where:
- The participant is receiving compelling benefit, benefit of drug restart exceeds risk, and no effective alternative therapy is available. Ethics Committee or Institutional Review Board approval of drug restart/rechallenge must be obtained, as required.
- If the restart/rechallenge is approved by the VSLC in writing, the participant must be provided with a clear description of the possible benefits and risks of drug administration, including the possibility of recurrent, more severe liver injury or death.
- The participant must also provide signed informed consent specifically for the IP restart/rechallenge. Documentation of informed consent must be recorded in the study chart.
- Study drug must be administered at the dose specified by the VSLC.
- Participants approved by the VSLC for rechallenge of IP must return to the clinic twice a week for liver chemistry tests for a minimum of one month and thereafter for as long as clinically indicated and then laboratory monitoring may resume as per protocol. If protocol defined stopping criteria for liver chemistry elevations are met, study drug must be stopped.

#### 5.5.1.3.2. *Drug Restart Following Transient Resolving Liver Events Not Related to IP*

Approval by the VSLC for drug restart or additional IM administration can be considered where:

- Liver chemistries have a clear underlying cause (e.g., biliary obstruction, hypotension and liver chemistries have improved to normal or are within 1.5 x baseline and ALT <3xULN). Ethics Committee or Institutional Review Board approval of drug restart/rechallenge must be obtained, as required.
- If restart/redosing of drug is approved by the VSLC in writing, the participant must be provided with a clear description of the possible benefits and risks of drug administration, including the possibility of recurrent, more severe liver injury or death.

- The participant must also provide signed informed consent specifically for the restart. Documentation of informed consent must be recorded in the study chart.
- Study drug must be administered at the dose specified by the VSLC.

Participants approved by the VSLC for restarting or re-dosing IP must return to the clinic once a week for liver chemistry tests for a minimum of one month and thereafter for as long as clinically indicated and then laboratory monitoring may resume as per protocol. If protocol defined stopping criteria for liver chemistry elevations are met, study drug must be stopped.

See Section 12.3, Appendix 3 for full guidance.

### 5.5.2. QTc Stopping Criteria

A participant who has a QTc interval  $>550$  msec considered causally related to IP will be withdrawn from the study. The QTc should be based on averaged QTc values of triplicate electrocardiograms obtained over a brief (e.g., 5 to 10 minute) recording period.

If an alternative cause of the QT prolongation is determined (e.g., participant receiving drug known to cause prolonged QT or TdP), the IP may be restarted (or continued) after consultation and agreement with the Medical Monitor.

The *same* QT correction formula *must* be used for *each individual participant* to determine eligibility for and discontinuation from the study. This formula may not be changed or substituted once the participant has been enrolled.

For example, if a participant is eligible for the protocol based on QTcB, then QTcB must be used for discontinuation of this individual participant as well.

Once the QT correction formula has been chosen for a participant's eligibility, the *same formula* must continue to be used for that participant *for all QTc data being collected for data analysis*. Safety ECGs and other non-protocol specified ECGs are an exception.

### 5.5.3. Virologic Failure

Only plasma HIV-1 RNA values determined by the central laboratory will be used to assess virologic failure.

### 5.5.4. Definition of Confirmed Virologic Failure

For the purposes of clinical management in this study, CVF is defined as:

Rebound as indicated by two consecutive plasma HIV-1 RNA levels  $\geq 200$  c/mL after prior suppression to  $<200$  c/mL.

